- h. The patient will record injection site reactions in the eDiary starting the day after injection and for 7 days following the injection. Injection site reactions reported by patients in the eDiary during day 1-7 following an injection should not be reported as an AE in the eCRF. Any injections site reactions reported after the 1 week recording period will be recorded as AEs in the eCRF.
- i. Patients will record insulin dose in the eDiary for 4 days prior each visit starting from Visit 2. Insulin dose collected at Visit 2 (for the 4 days prior to Visit 2) will be done by the Investigator and recorded in the eCRF.
- j. FGM during 2 weeks post visit for Visits 1, 6 and 7. Patients will be given instructions on when and where to return the device after the testing period. For instruction on how to return the Freestyle Libre Pro sensor, please refer to the Freestyle Libre Pro Worksheet.
- k. The number of self-reported severe hypoglycemia (defined as needing help from others and/or seizures and/or unconsciousness) should be recorded in the eCRF and each event will be recorded separately.
- l. See Procedure for MMTT in the Operations Manual
- m. Only applicable to patients completing their Visit 7 after 01 January 2020.
- n. Patients that have completely withdrawn from the study will be asked to return for a final visit at month 15, in order to achieve as complete as possible follow-up. See section 8.5 for further details.

Table 3 Schedule of Study Events, Extension Study Period

Event	V8 ^g Month 24
DAY	720 (±14)
General Physical Exam ^a	X
Neurological Assessment	X
Concomitant Medication	X
Vital signs (BP)	X
Pubertal Stage, if applicable ^b	X
eDiary use compliance	X
Insulin Dose Collected ^c	X
FreeStyle LibrePro, FGM ^d	X
AEs	X
Urine Pregnancy Test (menarchal females only)	X
Self-reported severe hypoglycemia ^e	X
QoL questionnaire	X
MMTT ^f	X
Blood Sampling for Safety, Genetics, Vitamin D levels and Immunology:	
Hematology	X
Clinical Chemistry	X
GAD65A titer	X
Vitamin D level	X
Covid-19 serological test	X
Other immunological parameters as specified in Section 6.4.2	X
Urine Analysis:	
Microalbuminuria	X
Creatinine	X
Blood Sampling for Diabetes Status:	
Fasting C-peptide	X
MMTT-induced C-peptide^f	X
HbA1c	X
Fasting Glucose	X
MMTT-induced Glucose^f	X

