7.1.1 Study Procedures

The study procedures and assessments are described in the section below and presented in detail in Section 9.1 (diabetes status assessments), Section 9.2 (safety), Section 9.3 (immunological assessments), Section 9.4 (genetic status assessments), Section 9.5 (vitamin D status), Section 9.7 (Quality of Life) Section 9.7 (pubertal stage, concomitant medication assessments), and Section 9.9 (demographics).

Recording and reporting of AEs are described in detail in Section 11.

The timing of all study events is shown in Table 2 and Table 3 in Section 7.1.

7.1.1.1 All Visits, Visit 1 through Visit 8

Note that the patient should attend all study visits in the morning following an overnight fast (>10 hours, water allowed). For patients with evidence of an infection (including fever), the complete visit should be postponed for 5 days or until the patient has recovered.

7.1.1.2 Timing of all visits, Visit 1 through Visit 8

The first visit, the screening visit (Visit 1) should be performed 14 to 28 days before planned Visit 2 (Baseline), when Vitamin D treatment starts. One month (30 days) later, at Visit 3, the first injection of Diamyd will be administered. For Visit 4 (second Diamyd administration), the visit date must be set in accordance with Visit 3 (i.e. the first Diamyd administration) so that the first and second Diamyd doses will be 30 days apart (± 5 days). For Visit 5 (third Diamyd administration) the visit date must be set in accordance with Visit 4 (i.e. the second Diamyd administration) so that the second and third Diamyd doses will be 30 days apart (± 5 days). For Visit 6, 7 and 8, the visit date must be calculated from baseline (Visit 2) ± 14 days.

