7.5 Management of the Disease

All patients will continue to receive intensive insulin treatment through their personal physicians via multiple daily injections of insulin or via insulin pump and should not use any oral or injected non-insulin pharmaceuticals for glycemic control. If, by mistake, such medication is introduced during the study, this is not a reason for discontinuation of the patient. The primary responsibility for diabetes management will be the treating or referring diabetes care provider, but the research study team will provide close additional support through interaction by phone as needed. Diabetes management will be monitored by the study staff with phone calls between study visits as needed. Patients will fill in their insulin doses 4 days before each visit in the patient diary.

The following diabetes treatment goals will be given to patients and treating physicians in accordance with the current recommendations of the American Diabetes Association (ADA) ²⁷

- Pre-meal glucose 4.4 to 7.2 mmol/L
- Bedtime/overnight glucose 5 to 8.3 mmol/L
- HbA1c <53 mmol/mol (Diabetes Control and Complications Trial [DCCT]-aligned)

These goals are only for guidance and are not considered as violating the protocol if not achieved, but it is regarded as important that every patient and treating physician make their best effort to achieve these recommendations.

The investigator/diabetes team/study nurse will provide support for T1D management by making scheduled phone calls to patients if HbA1c results are ≥ 53 mmol/mol at any study visit.

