8.5 Patient Withdrawal

In accordance with the Declaration of Helsinki, the investigator must explain to the patient that they have the right to withdraw from the study at any time, and that this will in no way prejudice their future treatment. The reason for any kind of withdrawal must be recorded on the appropriate section of the eCRF.

There will be two main categories for withdrawals from the study:

Complete withdrawal (i.e. stopping investigational product(s) and also continued efficacy and safety evaluations). In order to achieve as complete as possible 15 month follow-up, whenever feasible, patients that are considered for complete withdrawal should be asked if they could consider to return for a 15-month visit, preferable complete visit but as a minimum do the MMTT, C-peptide and HbA1c sampling, and collection of AEs. Attempts should be made to contact patients lost to follow-up with respect to this.

Standard reasons for withdrawing from further participation in the study and from the follow-up visits may be:

- Patient's decision (withdrawal of consent to participate)
- Patient lost to follow-up

Withdrawals from investigational product(s) (i.e. stopping one or several investigational products, but continuing follow-up visits, including efficacy and safety evaluations)

Standard reasons from withdrawing from taking further investigational product, but continuing follow-up visits and safety evaluations may be:

- Unacceptable AEs
- Patient request
- Investigator's discretion
- Patient lost to follow-up/non-attendance
- Intercurrent illness
- The patient becomes pregnant

Diamyd/placebo should not be given to the patient if the patient after inclusion in the study develops/experiences:

- Brain damage, epilepsy, head trauma, neurological disease
- Any active, serious hormonal disease other than T1D
- Other severe autoimmune disease (except celiac disease which is accepted for inclusion)
- Immune-suppressive treatment
- Cancer, cancer treatment
- Any other diabetes drugs other than insulin (and the combination regimen administered in this study)
- Any vaccination

- Drug/alcohol abuse
- Becomes pregnant or is no longer willing to use safe contraceptives during the study

Vitamin D/placebo treatment should not be continued if the patient after inclusion in the study develops/experiences:

- Symptoms of hypercalcemia such as tiredness, euphoria, drowsiness, nausea, weight loss, thirst, polyuria, nefrocalcinosis, renal failure
- Arrhythmia

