10.1.1 Method of Assigning Patients to Treatment Groups

A computer-generated randomization list will be produced by the IWRS system. After confirmation of eligibility at Visit 2 patients will be randomized in a 1:1 ratio (Arm 1:Arm 2) across all study sites. Randomization will be stratified by country and GAD65A level to ensure that an equal number of patients in respective age group are included in each arm.

- Arm 1: Diamyd + vitamin D
- Arm 2: Placebo for Diamyd + Placebo for vitamin D

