10.4 Concomitant Therapy

The patients will receive adequate therapy for concomitant diseases at the discretion of the investigator. Patients receiving a drug listed under exclusion criteria at screening should not be included in the study. Patients who are prescribed a drug listed in the exclusion criteria during the period between screening and first injection should be withdrawn from the study.

Any concomitant medication must be recorded in the eCRF. Note: if a new medication is introduced or an existing medication is changed due to a new medical condition or worsening of a pre-existing medical condition, the condition must be reported as an AE.

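### Section 10.4 withdraws patients from the study for an excluded drug up to the first injection, about a month after randomisation, in conflict with Sections 7.5 and 8.5

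*Protocol*

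**What the plan says.** **Section 10.4 (Concomitant Therapy).** Patients prescribed a drug from the exclusion list "during the period between screening and first injection should be withdrawn from the study". The sentence does not separate time before randomisation from time after it, and does not refer to Section 7.5 or 8.5.

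**Timing.** Section 10.1.1: "After confirmation of eligibility at Visit 2 patients will be randomized in a 1:1 ratio". Visit 2 is Day 1. Oral vitamin D or its placebo also starts then if the screening level is below 100 nmol/L. Section 7.1.1.2: "One month (30 days) later, at Visit 3, the first injection of Diamyd will be administered". The window for Visit 3 is Day 30 ± 5.

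**Section 7.5 (Management of the Disease)**, on non-insulin drugs for glycaemic control: "If, by mistake, such medication is introduced during the study, this is not a reason for discontinuation of the patient". Exclusion criterion 3 names the same drugs.

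**Section 8.5 (Patient Withdrawal).** "There will be two main categories for withdrawals from the study": complete withdrawal, and withdrawal from product, which means "stopping one or several investigational products, but continuing follow-up visits, including efficacy and safety evaluations". A further list opens with "Diamyd/placebo should not be given to the patient if the patient after inclusion in the study develops/experiences" and includes immunosuppressive treatment, diabetes drugs other than insulin, and any vaccination. The standard reasons given for complete withdrawal are the patient's decision and loss to follow-up.

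**After complete withdrawal.** Table 2, footnote n: "Patients that have completely withdrawn from the study will be asked to return for a final visit at month 15". Section 8.5 asks for this where feasible, with the meal test, C-peptide, HbA1c and adverse events as the minimum. Section 8.4 rules out replacing patients withdrawn after randomisation.

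**The concern.** A rule that stops an ineligible patient from entering is sound before randomisation, where it works as a screen failure. Section 10.4 carries the same rule about a month past randomisation, so an event after randomisation removes a patient whom the primary comparison should include.

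On the plain reading, that patient leaves before the first post-baseline mixed meal tolerance test (Month 6), would normally miss that test, and supplies the Month 15 value only by agreeing to come back. The mixed model for repeated measures in Section 13.2.3.1 cannot use a patient who has no post-baseline meal test. A patient withdrawn before Visit 3 who does not return has no scheduled post-baseline efficacy assessment either, and so falls outside the full analysis set defined in Section 13.2.1. The instruction itself would cause the loss, although every visit needed to avoid it is already scheduled.

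The protocol also gives sites conflicting orders. If a non-insulin antidiabetic drug is started by mistake on Day 15, 10.4 says withdraw and 7.5 says do not discontinue.

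**Working it through.** **1. How much of the 10.4 window follows randomisation**

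Inputs from Table 1 and Section 7.1.1.2:
- Screening to Visit 2: 14 to 28 days.
- Visit 2 (Day 1) to Visit 3 (Day 25 to Day 35): 24 to 34 days.

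Results:
- Total window: 14 + 24 = 38 days to 28 + 34 = 62 days.
- Smallest share after randomisation: 24 / (24 + 28) = 46%.
- Largest share: 34 / (34 + 14) = 71%.

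These are shares of calendar time, not of patients.

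**2. The rules side by side, for a patient randomised on Day 1 and prescribed the drug on Day 15**

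| Drug | Section 10.4 | Section 7.5 | Section 8.5 |
|---|---|---|---|
| Non-insulin antidiabetic, by mistake | Withdraw from study | Not a reason to discontinue | Withhold injection |
| Immunosuppressant | Withdraw from study | Silent | Withhold injection |

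Section 7.4 counts a patient as included from consent at Visit 1, so Day 15 lies within the study for both 7.5 and 8.5. The first row is a direct contradiction between 10.4 and 7.5. Against 8.5 the difference is an inconsistency: 8.5 provides for stopping product while follow-up continues, but its reasons for complete withdrawal are introduced as possibilities, so the list is not closed. After the first injection, 8.5 would only withhold further doses for these drugs. The protocol gives no reason for treating an already randomised patient differently before that injection.

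**3. Size**

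Inputs from Section 13.1: N = 106 randomised 1:1, two-sided 0.05, power 90%, loss 10%, and 0.134 and 0.20 on the ln(X+1) scale. I take 0.134 as the between-arm difference, because that reading reproduces the stated size.

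The plan's own figure first, by the normal approximation:
- n per arm = 2 × (1.960 + 1.282)² × (0.20 / 0.134)² = 46.8, rounded up to 47.
- Allowing for loss: 47 / 0.90 = 52.2, rounded up to 53 per arm, total 106. This agrees with Section 13.1.

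Power after further losses, by the two-sample t-test (noncentral t), with effect 0.134 / 0.20 = 0.67 SD, noncentrality 0.67 × √(n/2) for n per arm, and evaluable N = 106 × 0.9 − k:

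| Lost beyond the 10% (k) | Evaluable N | Power |
|---|---|---|
| 0 | 95.4 | 89.9% |
| 2 | 93.4 | 89.3% |
| 4 | 91.4 | 88.7% |
| 6 | 89.4 | 88.0% |

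The values of k are assumptions, since the protocol gives no rate of such prescriptions. If these losses stay within the planned 10%, power is unchanged.

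**The case against.** The strongest reply is that 10.4 can be read together with 8.5. Section 8.5 lists stopping product as one kind of withdrawal from the study, so 10.4 might mean only that the injections are not given, and for antidiabetic drugs the specific rule in 7.5 might be taken to override the general one. That reading is possible. But 10.4 does not point to 8.5, and the sentence before it concerns patients who should not enter the study at all, so ending participation is the more natural meaning. If product only was intended, the change below simply says so.

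Second, the endpoint is partly protected. Completely withdrawn patients are to be asked back at Month 15, and the minimum visit includes the meal test. This stands: the primary value is put at risk, not lost by rule. The return is voluntary, however, and the Month 6 test would normally be missed.

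Third, loss from the full analysis set is narrow. HbA1c and fasting C-peptide are scheduled at Visit 3, so a prescription discovered there would normally come with a post-baseline efficacy value. Exclusion needs both withdrawal before Visit 3 and no return. That is right, although a patient who qualifies this way and has no later meal test still adds nothing after baseline to the primary model.

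Fourth, the numbers are small and illustrative. Many such patients are screened out, the post-randomisation window is about a month, and the power figures use an unadjusted t-test where the plan uses a baseline-adjusted mixed model. Only blinded oral treatment has been given before Visit 3, so nothing suggests that withdrawals would differ by arm. All of this stands and limits the weight of the point. It does not remove the conflict between the sections.

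**Conclusion.** The concern holds. As worded, Section 10.4 withdraws randomised patients because of an event after randomisation, contradicts 7.5 for non-insulin antidiabetic drugs, and is inconsistent with 8.5. The timing and the conflict come straight from the text. The loss of follow-up depends on sites taking 10.4 at its plain meaning and on patients not returning at Month 15.

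The size is small: about 2 percentage points of power (89.9% to 88.0%) at the largest assumed loss of six patients beyond the 10% allowance with none returning, and nothing if the losses stay within it. No bias in either direction is shown. The reason to act is that the loss is avoidable and the instructions conflict. The change should be made, but the trial does not stand or fall on it.

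**What to change.** Reword Section 10.4 so that withdrawal from the study for a newly prescribed excluded drug applies only before randomisation, with the patient counted as a screen failure. From randomisation onward:

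- record the drug as a protocol deviation;
- use Section 8.5 to decide whether Diamyd/placebo or vitamin D/placebo is withheld;
- keep all scheduled visits, including the Month 6 and Month 15 meal tests.

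Add a cross-reference from 10.4 to 7.5 and 8.5. The cost is one sentence and the cross-reference in a protocol amendment. No procedure is added, because the visits are already scheduled, and for the drugs that 8.5 lists the injections are still withheld.

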10.5 Post Study Treatment

No study medication will be offered to the patients after completion of the last injection. Patients will thereafter receive therapy at the discretion of the investigator and according to prescriptions.

11 ADVERSE EVENTS

11.1 Definitions of Adverse Events (AE)

An AE is defined as any untoward medical occurrence in a subject during a clinical study administered a medicinal product and which does not necessarily have a causal relationship with this treatment(s).

An AE can therefore be any unfavorable and unintended clinical sign or symptom, any illness or disease, which develops or worsens in intensity during the course of the trial. It also includes an abnormal laboratory finding, if e.g., the abnormality results in trial withdrawal, is serious, is associated with clinical signs or symptoms, or is considered being of clinical relevance.

It could also include accidents and reasons for changes in medication (drug and/or dose), any medical/nursing/pharmacy consultation and admission to hospital/surgical operations.

Any new findings, clinically significant laboratory values or worsening of pre-existing condition must be reported as an AE by the investigator, whether or not considered related to the medicinal product(s).

Note that hospital admission and/or surgical operations for illness, which existed before the study drug was given or the subject was enrolled in the clinical trial and did not worsen during the study, are not AEs.

T1D-related events

The number of self-reported episodes of severe hypoglycemia (Severe hypoglycemia defined as needing help from others and/or seizures and/or unconscious) between baseline and subsequent visits will be collected in the eCRF. Hypoglycemia, changes in C-peptide, changes to insulin dosage, and increases in HbA1c/blood glucose will not be reported as AEs unless the definition of SAEs is met.

11.2 Seriousness

A SAE is defined as: an AE that is fatal, life-threatening, significantly or persistently disabling, requiring hospitalization or prolongation of existing hospitalization or that is a congenital anomaly or birth defect.

These characteristics/consequences have to be considered at the time of the event. For example, regarding a life-threatening event, this refers to an event in which the subject was at risk of death at the time of the event; it does not refer to an event which hypothetically might have caused death if it were more severe.

Some medical events may jeopardize the subject or may require an intervention to prevent one of the above characteristics/consequences. Such events (referred to as important medical events) should also be considered as serious in accordance with the definition.

11.3 Intensity

Mild: The AE is transient and easily tolerated.

- Moderate: The AE causes the patient discomfort and interrupts the patient's usual activities.
- Severe: The AE causes considerable interference with the patient's usual activities, and may be incapacitating or life-threatening.

Note: a distinction should be drawn between serious and severe AEs. The term severe is used to describe the intensity of the event and the event does not necessarily need to be considered serious. The term serious is based on the patient/event outcome or action and serves as a guide for defining regulatory reporting obligations.

11.4 Relationship to Study Medication

Relationship to study medication will be assessed for the two treatments (Diamyd and Vitamin D) separately. AEs with a causal relationship assessment of Unlikely related, Possibly related and Probably related will be considered to be Adverse Reactions.

Not related: This category is applicable to those AEs which, after careful medical consideration at the time they are evaluated, are judged to be clearly and incontrovertibly due to extraneous causes (disease, environment, etc.) and do not meet the criteria for study medication relationship listed under remote, plausible or probable.

Unlikely related: Time relationship non-existent or doubtful and/or other factor(s) certain or probable to have been causative.

Possibly related: Time relationship exists. Other possible causative factor(s) may exist (e.g., concurrent disease or concomitant medication). Improvement on dechallenges or dose reduction may or may not have been seen.

Probably related: Time relationship exists. No other possible causative factor(s) may exist (not reasonably explained by the patient's known clinical state or concomitant medication). Improvement on dechallenges or dose reduction (if performed) has occurred. Recurrence of symptoms on rechallenge (if performed) has occurred. A specific laboratory investigation (if performed) has confirmed the relationship.

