13.2.3.3.1 Secondary Safety Variables

Adverse events:

AEs will be coded according to the MedDRA system and tabulated by System Organ Class (SOC) and by preferred term.

A summary table will be presented with total number and No. of patients with:

- AEs
- serious AEs
- related AEs
- AE leading to discontinuation

AE will only be counted once within each patient on a preferred term level.

The total number of patients with at least one AE and the number of AEs will be derived and summarized by SOC and preferred term.

AEs will also be tabulated versus intensity and relationship to treatment (classified as related for outcomes “Remote”, “Plausible” and “Probable” and not related for outcome “Unrelated”. If a patient has more than one event classified with the same preferred term, then the worst intensity and the worst relationship will be used. In this table, patients having AEs will be identified by their patient number.

A treatment-emergent AE (TEAE) is an event emerging after treatment start or worsening during treatment. Hence, events with an onset time on or after the time of treatment start are treatment-emergent. Only TEAEs will be included in summary tables. Pre-treatment AEs will be listed.

Treatment-emergent serious adverse events (TESAEs) will be listed separately.

In listings of AEs the relative day of occurrence will be given. Relative day will be calculated as (Date of first administration of IMP – AE start date) + 1 for AEs occurring on date of first administration of IMP or later and as (Date of first administration of IMP – AE start date), otherwise.

AEs will be presented for the main study period and for the whole study period.

Other safety endpoints:

All other safety endpoints will be presented using summary statistics. These presentations will be done for the Main Study Period and the whole study period where only the patients that participated in the Extension Study Period will be included. For laboratory measurements and vital signs change from baseline will also be summarized. Shift tables will present shifts for all endpoints for which normal/abnormal (Not Clinically Significant/Clinically Significant [NCS/CS]) judgements exist.

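### Events graded Unlikely related count as adverse reactions and enter the related-AE summary, although that grade overlaps with Not related at the cut

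*Protocol*

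**What the plan says.** Section 11.4 has four grades: Not related, Unlikely related, Possibly related and Probably related. The top three are grouped: "AEs with a causal relationship assessment of Unlikely related, Possibly related and Probably related will be considered to be Adverse Reactions". Unlikely related is defined as "Time relationship non-existent or doubtful and/or other factor(s) certain or probable to have been causative". Not related is reserved for events that are beyond dispute due to outside causes and that "do not meet the criteria for study medication relationship listed under remote, plausible or probable". The words remote and plausible are not grade names in that section.

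Section 13.2.3.3.1 lists related AEs as a row of the AE summary table and adds: "AEs will also be tabulated versus intensity and relationship to treatment". Relationship is reduced to two classes there, "classified as related for outcomes “Remote”, “Plausible” and “Probable” and not related for outcome “Unrelated". For a patient with repeated events of one preferred term, "the worst intensity and the worst relationship will be used".

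Section 11.4 also says: "Relationship to study medication will be assessed for the two treatments (Diamyd and Vitamin D) separately". Section 13.2.3.3.1 does not say whether the tables are laid out per product.

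**The concern.** The related count is read as the investigators' blinded opinion of what the treatment caused. If it includes events that the same investigators put down to another cause, it measures something else. Background illness should occur at about the same rate in two randomised, blinded arms. Adding it to both counts brings the two proportions closer together.

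The definitions make this more likely. The bar for Not related is very high, so an ordinary intercurrent illness may well be graded Unlikely related. Under the plan that choice alone decides whether the event is an adverse reaction. Two investigators with the same view of the cause can therefore produce different related-AE counts.

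**Working it through.** The protocol attaches no figure to this point, so there is none to reproduce. The check is a comparison of the texts, followed by an illustration of direction.

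**Step 1: the boundary inside section 11.4.** Take an event with a certain other cause.

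- It fits Unlikely related, because that definition includes other factors that are certain.
- It also fits the first half of Not related, which describes an event clearly due to something else.
- The second half of Not related does not settle the matter. It excludes events that meet the criteria listed under remote, plausible or probable. If remote means Unlikely related, the clause read literally sends the event to Unlikely related, and so among the adverse reactions.

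The overlap therefore lies exactly at the cut.

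**Step 2: the labels.** The older words survive inside the Not related definition, so the mapping can be inferred:

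| Section 13.2.3.3.1 | Section 11.4 | Class |
|---|---|---|
| Unrelated | Not related | not related |
| Remote | Unlikely related | related |
| Plausible | Possibly related | related |
| Probable | Probably related | related |

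Under this mapping both sections draw the same line. The mismatch is a matter of wording and does not move the cut. It does confirm that Unlikely related events enter the related outputs by a stated analysis rule.

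**Step 3: the effect within a patient.** The worst-relationship rule selects the highest rating among repeated events of one preferred term. One Unlikely related rating among several Not related ones makes that preferred term related for the patient.

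**Step 4: direction of the effect (assumed inputs only).** Let p be the share of patients with a Possibly or Probably related AE. Let u be the share with at least one Unlikely related AE, taken as equal in both arms and independent of p. The share counted as related is then 1 − (1 − p)(1 − u), and the risk difference shrinks by the factor (1 − u).

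With p = 0.30 active and 0.10 placebo:

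- u = 0: 0.30 / 0.10 = 3.0
- u = 0.2: 1 − 0.7 × 0.8 = 0.44; 1 − 0.9 × 0.8 = 0.28; ratio 1.57, difference 0.16
- u = 0.4: 1 − 0.7 × 0.6 = 0.58; 1 − 0.9 × 0.6 = 0.46; ratio 1.26, difference 0.12

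With p = 0.40 and 0.15:

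- u = 0: ratio 2.67, difference 0.25
- u = 0.2: 0.52 and 0.32; ratio 1.63, difference 0.20
- u = 0.4: 0.64 and 0.49; ratio 1.31, difference 0.15

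None of these rates comes from the protocol. If Unlikely related events fall mainly in patients who already have a Possibly or Probably related event, the dilution is smaller.

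**The case against.** The strongest reply is that the cut is deliberately inclusive and the same in both sections. Unlikely related also covers doubtful timing and a merely probable other cause, so some of these events could be true reactions that a narrower count would miss. This stands. It is wrong to say that every Unlikely related event is by definition not a reaction. What remains is the part of the grade with no time relationship or a certain other cause, and its overlap with Not related. It is also a reason to keep the inclusive count and not to replace it.

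The reach is limited as well. AEs overall, serious AEs, AEs leading to discontinuation, and tables by system organ class and preferred term do not use the relatedness cut. Injection site reactions are a separate safety endpoint. No test of related AEs is specified, and causality is recorded for every AE, so a narrower count could be recovered later. All of this stands. It confines the point to the related-AE outputs and the adverse-reaction definition.

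A reader might infer more in two places:

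- **That the worst-relationship rule merges the Diamyd and vitamin D ratings, so that related events cannot be attributed to either product.** The documents do not support this. The rule concerns repeated events of one preferred term in a patient. The protocol is silent on tables per product, and that detail may be in the statistical analysis plan. Both active products are also given together against double placebo, so the randomised comparison could not separate them under any table layout.
- **That the analysis uses a different scale from the one investigators complete.** The one-to-one mapping in step 2 shows leftover terminology and the same cut.

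**Conclusion.** The point holds in a narrow form. Section 11.4 classes as adverse reactions a grade whose definition partly overlaps with Not related, and section 13.2.3.3.1 puts that grade into the related-AE count. The likely consequence is extra background events in both arms and a related-AE contrast pulled towards no difference.

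That direction rests on Unlikely related events being about equally common in the two blinded arms and falling partly in patients without a Possibly or Probably related event. The size is unknown. The ratios in step 4 show the mechanism and are not an estimate for this trial. Efficacy results and the other safety outputs are not touched. This is an inexpensive improvement to one descriptive safety result.

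**What to change.** 1. Use one set of grade names in sections 11.4 and 13.2.3.3.1, including inside the Not related definition.
2. Redraw the definitions of Not related and Unlikely related so that an event with a certain other cause or no time relationship fits only one of them.
3. Tabulate the four grades separately by arm. Show a Possibly/Probably count beside the inclusive Unlikely/Possibly/Probably count.
4. Leave expedited-reporting practice unchanged.

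Optionally, state whether relationship is tabulated per product, since the separate ratings already exist. This is a presentation choice and may already be settled in the statistical analysis plan.

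The cost is wording in two sections and a few more table columns, from data already collected. The report must also explain two related-AE counts, one lower than the other.
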